3.5.2 Neoadjuvant Cohort

	Screening	Week 0 (Baseline)	Week 2 (+/- 3 days)	Week 4 (+/- 3 days)	Week 6 ⁶ (+/- 3 days)	Week 8 ⁶ (+/- 3 days)	Post study treatment visit ⁷	Safety Visit 6-8 weeks after treatment discontinuation ⁴
Treatment								
Vaccinia- PROSTVAC		X						
Fowlpox- PROSTVAC			X	X		X		
Nivolumab 240 mg (Flat dose)			X	X	X	X		
Assessments								
History and PE, and Weight	X ²	X ³	X	X	X	X	X	X
Height	X ²							
ECOG Performance Score	X ²	X ³	X	X	X	X		X
ECG	X ²	X ³						
HLA class I profile		X ³						
Pathologic confirmation of dx ¹	X ¹							
Labs (see Sections 2.1.4 and 2.2.1)	X ²	X ³						
Labs: CBC, TSH,			X	X	X	X	X	X

Abbreviated Title: Prostvac-Nivo in prostate ca

Version Date: 01.10.2023

	Screening	Week 0 (Baseline)	Week 2 (+/- 3 days)	Week 4 (+/- 3 days)	Week 6 ⁶ (+/- 3 days)	Week 8 ⁶ (+/- 3 days)	Post study treatment visit ⁷	Safety Visit 6-8 weeks after treatment discontinuation ⁴
amylase, lipase, PSA, PT, PTT and the following panels: acute care, mineral, hepatic								
Research labs: 6 green tops (PBMCs) and 2 SSTs (serum).		X	X	X			X	X
Gene expression profiling (PaxGene tube)		X					X	
Immunology Assays/TBNK		X	X	X	X	X	X	
Prostate biopsy		X						
Serum PSA	X	X	X	X	X	X	X	
MRI prostate		X					X	
PT/PTT/INR	X						X	

¹Pathologic confirmation will be obtained any time prior to enrollment

²Screening assessments obtained within 35 days prior to enrollment

³Baseline assessments obtained within 16 days prior to enrollment (these tests will not need to be repeated if they were done at screening within the appropriate timeframe)

⁴Assessment of SAEs at approximately 100 days (\pm 1 week) after nivolumab discontinuation. Assessment may be conducted by phone if the participant cannot come to the NIH. Assessments may also be performed by a local provider.

⁵A standard of care radical prostatectomy will be performed between week 5 and week 12 week to allow for logistical constraints, but ideally as close to week 9 as possible. This may occur at NIH or at an outside institution.

Abbreviated Title: Prostvac-Nivo in prostate ca

Version Date: 01.10.2023

⁶If surgery is scheduled earlier than 9 weeks after initial dosing, the 6 and 8 week dosing and study visits/procedures may be skipped and surgery may be done as early as week 5.

⁷ This visit should occur one week after the final planned study immunotherapy treatment (-3/+7 days).

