1.1.2 Secondary Objectives

- To determine the change in peripheral PSA-specific T cells in participants treated with PROSTVAC and nivolumab.
- To document any intraprostatic T_{reg} cell infiltration with CD4+FOX-P3 staining.
- To document any PSA changes secondary to immune treatment, including rate of biochemical recurrence after prostatectomy.
- To document any MRI changes secondary to treatment (including changes in ADC mapping)
- To evaluate changes in PDL-1 expression in tumor.
- To document pathologic responses (including pathologic CR).
- To evaluate changes in immune cell subsets in the periphery.
- To evaluate changes in soluble immune mediating factors (such as cytokines, etc.) in sera.
- To evaluate changes in circulating tumor cells levels (for CRPC cohort only)
- Safety (for localized prostate cancer cohort)

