2.2.1 Treatment Assignment Procedures

Cohorts

Number	Name	Description
1	Cohort 1	Men with Prostate Cancer

Arms

Number	Name	Description
1	Lead-in CRPC Cohort	PROSTVAC-V on week 0 followed by booster injection called PROSTVAC-F on 2, 4, and 8 weeks. Nivolumab will be administered every 2 weeks, starting at week 2. When administered on the same day, the preferred order of administration is PROSTVAC first followed by nivolumab. Participants will undergo restaging scans on week 12 prior to receiving treatment. If no PD, option to continue treatment with nivolumab every 2 weeks and PROSTVAC-F every 4 weeks until intolerance or progression (evaluated radiographically every 12 weeks). Participants who remain on protocol beyond 1 year will have the option of extending the nivolumab dosing interval to every 4 weeks.
2	Neoadjuvant Cohort	PROSTVAC-V on week 0 followed by booster injection called PROSTVAC-F on 2, 4 and 8 weeks. Nivolumab will be administered on weeks 2, 4, 6, and 8. When administered on the same day, the preferred order of administration is PROSTVAC first followed by nivolumab. Participants will undergo prostatectomy on week 9. (If surgery is scheduled earlier than 9 weeks after initial dosing, the 6 and 8 week dosing may be skipped and surgery may be done as early as week 5.)

Arm Assignment

Participants in cohort 1 will be assigned to arm 1 until the expected number of participants enrolled (n=10), then participants will be assigned to arm 2 (n=17).

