4 CONCOMITANT MEDICATIONS/MEASURES

Subjects must inform the investigators of the current or planned use of all other medications during the study (including prescription medications, vitamins, herbal and nutritional supplements, and over-the-counter medications).

Anti-emetics, stool softeners and antidiarrheal agents may be administered as required but are not anticipated to be needed and should not be used prophylactically on the first cycle. The selection of the specific antiemetic regimen is at the discretion of the treating physician. Antiemetic regimens will not include steroids.

Other supportive care with blood components, antibiotics, analgesics, general medical therapy, etc., will be delivered as required. Any participants taking antibiotics for an active infection must complete that course of therapy and be free of evidence of further infection before receiving any immunotherapy treatment. Antibiotics for prophylaxis are allowed while on treatment.

Concurrent systemic corticosteroid use (daily or every other day for continued use > 14 days) should be avoided within 14 days before the first planned dose of PROSTVAC. Use of inhaled steroids, nasal sprays, and topical creams for small body areas is allowed. Limited use of steroids is allowed on study (e.g., for immune related adverse events or for premedication for imaging).

Symptomatic anemia should be treated with appropriate red blood cell or erythropoietin support.

Thrombocytopenia should be treated conservatively. In the absence of bleeding or a planned invasive procedure, platelet transfusions should be given for a platelet count below 10,000/mm³. If invasive procedures are planned or the participant develops bleeding, platelet transfusions should be administered in accordance with the standard of practice, usually maintaining a platelet count of > 50,000/mm³.

Any evidence of disseminated intravascular coagulation (DIC), hemolytic uremic syndrome (HUS), or thrombotic thrombocytopenic purpura (TTP) including thrombocytopenia, hemolytic anemia, renal failure, fever or neurologic changes should be thoroughly evaluated and closely monitored and supported as clinically indicated.

A standard of care radical prostatectomy will be performed between week 5 and week 12 to allow for logistical constraints, but ideally as close to week 9 as possible. This may occur at NIH or at an outside institution. Surgical specimens will be requested for research use (Section 5).

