5 CORRELATIVE STUDIES FOR RESEARCH

5.1 IMMUNE CELL INFILTRATE (TISSUE SPECIMENS)

Slides made from prostate biopsy specimens (collected at baseline) and prostatectomy specimens (collected at surgery performed after last dose of vaccine) will be stained for CD4 and CD8 cells and digitized for analysis of immune cell infiltrate. Other markers such as CD4/FoxP3 may also be stained for further correlative studies. These studies will be performed by the Laboratory of Tumor Immunology and Biology. At a minimum, 5 slides from one biopsy core confirmed to contain cancer will be needed for baseline quantification. Attempts will be made based on anatomic location notation or when available, MRI based location, to correlate biopsy location with pathologic location on prostatectomy specimens. When feasible, quantitation will be performed in triplicate. Quantitation will be reported as number of stained cells per micron squared of surface area. Wilcoxon matched pair signed rank test, Friedman test with Dunn's multiple comparisons, or alternative statistical models will be used as appropriate. Aperio ScanScope digital scanner systems with Aperio ImageScope software algorithms will be used. Manual quantitation will be performed in case of software malfunction. Isotype antibodies

negative controls will be included in all runs. Tonsil or lymph node tissue will be positive control for CD4 and CD8. Slides will be developed with primary and secondary antibodies per manufacturer specifications for visualization of cells.

Peripheral Blood Correlative Studies for Research/Pharmacokinetic Studies

Blood Studies	Blood Tube/Comments**	Destination
CBC with differential	One light lavender tube	CC Department of Laboratory Medicine (DLM)
Hepatic Panel, Acute Care Panel	One 4 mL SST	CC DLM
Anti-HIV-1/2	One 8 mL SST	CC TTV lab
PT/PTT/INR	One 4.5 mL citrate blue top	CC DLM
HBs Antigen Screening	One 8 mL SST	CC Department of Transfusion Medicine (DTM)
Anti-HCV Antibody	One 4 mL SST	CC DLM
Prostate Specific Antigen	One light lavender tube	CC DLM
Lymphocyte Phenotyping, TBNK	Six 10 mL Na Heparin tubes Two 8 ml SST tubes	NCI-Frederick [name]
Gene expression profiling* lab)	Two 2.5 mL RNA PaxGene tubes	Blood Processing Core ([name]

*RNA PaxGene to be drawn only on the weeks of biopsies or standard of care prostatectomy

** Please note that tubes and media may be substituted based on availability with the permission of the PI or laboratory investigator.

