5.1.4 MRI study

If logistically feasible, an MRI will be performed at baseline before the first vaccine administration and after the last vaccine administration as part of the pre-operative workup in the neoadjuvant cohort. This will be done to assess for changes in the imaging characteristics of the prostate cancer pre and post vaccination.

Prior to entering the scanner, the participant will answer the standard MRI safety checklist administered to all participants undergoing MRI in the Clinical Center to ensure that it is safe to perform an MRI. Images will be reviewed for lesions suspicious for prostate cancer. Pre and post-vaccine images will be compared to assess for changes seen on MRI. These studies will be performed by the NCI Molecular Imaging Program.

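### On the planned schedule the neoadjuvant post-treatment blood visit falls on the day of prostatectomy, and nothing requires the blood to be drawn first

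*Combined protocol and SAP*

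**What the plan says.** The timing rules for the neoadjuvant cohort stand in several places.

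- **Visit.** Footnote 7 of Section 3.5.2: "This visit should occur one week after the final planned study immunotherapy treatment (-3/+7 days". The visit carries PSA, research PBMC and serum, PaxGene, immunology assays/TBNK, coagulation tests and the prostate MRI.
- **Last dose.** Section 2.2.1: "Nivolumab will be administered on weeks 2, 4, 6, and 8".
- **Surgery.** Section 2.2.1: "Participants will undergo prostatectomy on week 9". Section 4 gives a range: surgery "will be performed between week 5 and week 12 to allow for logistical constraints, but ideally as close to week 9 as possible". Footnote 6 of Section 3.5.2 adds a short course, in which "the 6 and 8 week dosing and study visits/procedures may be skipped and surgery may be done as early as week 5".
- **MRI.** Section 5.1.4 places the second MRI "after the last vaccine administration as part of the pre-operative workup in the neoadjuvant cohort", if logistically feasible.
- **PaxGene.** The blood table in Section 5.1 has its own rule: "RNA PaxGene to be drawn only on the weeks of biopsies or standard of care prostatectomy".
- **Endpoints.** Section 1.1.2 lists "To document any PSA changes secondary to immune treatment" among the secondary objectives, with changes in PSA-specific T cells, peripheral immune subsets and soluble factors in serum. Section 10 names no visit for the PSA and peripheral immune endpoints and does not say how blood drawn after surgery is handled.

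**The concern.** The change from baseline in the blood endpoints is meant to describe the vaccine and nivolumab. A sample drawn after prostatectomy also reflects the operation: the main source of PSA is gone, and leukocytes and cytokines can move with surgical trauma. If the window allows both kinds of sample, a compliant data set can mix pre-operative and post-operative values under one visit label. With 17 evaluable men planned, a few such samples could shift a summary of change. Surgery may also take place at an outside institution (Section 4), so coordination of the draw with the operation should not be left to assumption. A sample drawn too late cannot be replaced.

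**Working it through.** **The plan's own figure.** The one design figure for this cohort is 80% power for the tissue comparison: 17 versus 26 men, a 1.0 SD difference, two-sided alpha 0.025 (Section 10). The noncentrality is 1/√(1/17 + 1/26) = 3.21 with 17 + 26 − 2 = 41 degrees of freedom, and the exact t-test power is 80.7%. The figure reproduces. It rests on biopsy and prostatectomy tissue, so the timing of blood draws does not enter it.

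**Day count.** Take week w as day 7w, last dose on day L and surgery on day S.

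- Target day = L + 7. Window = L + 4 to L + 14, which is 11 days.
- For S inside the window, days before surgery = S − (L + 4), and days after surgery = (L + 14) − S.

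| Last dose L | Surgery S | Target | Window | Before | On | After |
|---|---|---|---|---|---|---|
| 56 (week 8) | 63 (week 9) | 63 | 60–70 | 3 | 1 | 7 |
| 28 (week 4) | 35 (week 5) | 35 | 32–42 | 3 | 1 | 7 |
| 56 | 64 | 63 | 60–70 | 4 | 1 | 6 |
| 56 | 65 | 63 | 60–70 | 5 | 1 | 5 |
| 56 | 66 | 63 | 60–70 | 6 | 1 | 4 |
| 56 | 70 | 63 | 60–70 | 10 | 1 | 0 |
| 53 | 63 | 60 | 57–67 | 6 | 1 | 4 |
| 59 | 63 | 66 | 63–73 | 0 | 1 | 10 |

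The last two rows use the ±3-day window on the week 8 dose and count from the actual dose day. With surgery after day 70 and a day-56 dose, the whole window is pre-operative.

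**Can the later visit substitute?** The safety visit is 6 to 8 weeks after treatment ends.

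- Full course: 56 + 42 = day 98 to 56 + 56 = day 112. The surgery range ends at week 12, day 84.
- Short course: 28 + 42 = day 70 to 28 + 56 = day 84. That course applies to surgery before day 63.

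For surgery inside the stated range, the safety visit is post-operative on both courses.

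**What other draws exist (Section 3.5.2).**

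- Research PBMC/serum: weeks 0, 2 and 4, this visit and the safety visit. On the full course, this visit is the only one after week 4 that can precede surgery.
- PaxGene: week 0 and this visit only.
- PSA and immunology/TBNK: also at weeks 2, 4, 6 and 8. Week 8 is a pre-operative fallback on the full course, and week 4 on the short course. Each is scheduled at the last dosing visit, so it cannot show the effect of that dose.

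**PaxGene rules side by side.** Section 5.1 confines the draw to weeks of biopsy or prostatectomy. Sections 2.1.1 and 2.3.2 let a man enter on existing tissue without an on-study biopsy; Section 5.1 then gives him no baseline draw, while the calendar shows one at week 0. At the other end, for surgery on day 84 after a day-56 dose, the calendar window closes on day 70, which is 84 − 70 = 14 days earlier. The prostatectomy-week rule and the calendar cannot both be met.

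**The case against.** The strongest reply is that the visit is plainly meant to be pre-operative. A prostate MRI is ticked in the same column, Section 5.1.4 calls it part of the work-up for surgery, and the separate coagulation row is ticked only at screening and at this visit. That is a fair reading of intent. It does not bind the blood draws: the MRI is conditional on logistics, and the PaxGene rule names a week without saying before or after the operation.

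Surgery may also be as late as week 12, so the overlap is not universal. This stands, and the table shows how quickly it fades. The documents nevertheless steer surgery towards week 9, which is the case with the most overlap on nominal dosing.

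A reader might infer that no pre-operative PSA exists at the end of treatment. The calendar does not support that, given the values through week 8. The tube list for TBNK in Section 5.1 matches the research draw in number and type, so week 6 and 8 draws might also supply cells and serum; but the research row is not ticked at those weeks, so the plan does not say so.

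A reader might also infer that the plan will report surgery as a drug effect. Nothing directs that. The PSA objective expressly includes recurrence after prostatectomy, so some post-operative PSA belongs in it, and late draws can be identified by comparing draw and surgery dates. What remains is that Section 10 does not say what to do with them.

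**Conclusion.** The concern holds on the planned schedule. With surgery one week after the last dose, the target day is the day of surgery and 7 of 11 compliant days are post-operative. This assumes week 9 means day 63 and dosing on the nominal day. After a day-56 dose, most of the window is post-operative only for surgery up to day 64; on day 65 it is 5 of 11, and from day 70 it is none.

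The exposure is greatest for PaxGene and, on the full course, research PBMC/serum. It is smaller for PSA and immunology/TBNK. Only secondary and correlative endpoints are affected. A reader might extend the point to the primary tissue comparison, but that comparison uses no sample from this visit. Nor can the size of a surgical fall in PSA be stated, because the documents give no clearance rate. This is an inexpensive correction to make explicit what the calendar seems to intend, and it does not call the design into question.

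**What to change.** - **Footnote 7, Section 3.5.2:** keep the interval from the last dose and add that the visit takes place before prostatectomy in every case, with the window closing at surgery if surgery falls inside it.
- **Section 10:** state that blood drawn after prostatectomy is not used as the post-treatment value for change from baseline, and that for PSA and TBNK the last pre-operative on-treatment value is used where needed. Post-operative PSA remains available for biochemical recurrence.
- **Section 5.1:** reconcile the PaxGene footnote with the calendar, so that week 0 and the pre-operative visit apply whether or not an on-study biopsy is done.

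No visit or sample is added, and power is unchanged. The cost is tighter scheduling: when surgery is one week after the last dose, days 60 to 62 remain on the full course (3 days), or 4 days if a draw before incision on the day of surgery counts. For men already treated, comparing draw dates with surgery dates would show which samples the rule affects.

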3.6 COST AND COMPENSATION

3.6.1 Costs

NIH does not bill health insurance companies or participants for any research or related clinical care that participants receive at the NIH Clinical Center. If some tests and procedures are performed outside the NIH Clinical Center, participants may have to pay for these costs . Medicines that are not part of the study treatment will not be provided or paid for by the NIH Clinical Center.

3.6.2 Compensation

Participants will not be compensated on this study.

3.6.3 Reimbursement

The NCI will cover the costs of some expenses associated with protocol participation. Some of these costs may be paid directly by the NIH and some may be reimbursed to the participant/guardian as appropriate. The amount and form of these payments are determined by the NCI Travel and Lodging Reimbursement Policy.

3.7 CRITERIA FOR REMOVAL FROM PROTOCOL THERAPY AND OFF STUDY CRITERIA

Prior to removal from study, effort must be made to have all subjects complete a safety visit approximately 4-5 weeks for Lead-in mCRPC cohort and 6-8 weeks for neoadjuvant cohort) following the last dose of study therapy and at approximately 100 days after nivolumab discontinuation for both cohorts.

3.7.1 Criteria for removal from protocol therapy

Participants will be removed from treatment for the following:

- Grade 2 or greater toxicity attributed to treatment that does not resolve to grade 1 within 42 days from time of scheduled treatment except as described in Section [3.3](#).
- Grade 2 or greater autoimmune disease that threatens vital organs.
- Intercurrent illness or medical circumstances. If at any time the constraints of this protocol are detrimental to the participant's health, the participant may be removed from protocol therapy and reasons for withdrawal will be documented.
- Greater than 3-month delay in the performance of radical prostatectomy from week 12.
- Completion of protocol therapy
- Participant requests to be withdrawn from active therapy
- Investigator discretion
- Clinical or confirmed radiographic progression of disease (for CRPC Cohort only) (irPD)

3.7.2 Off-Study Criteria

1. Patient is off-treatment and has agreed to be followed on a long-term therapy protocol as outlined in Section [3.9](#) or has completed the study follow up period.

2. The study is stopped.
3. Participant requests to be taken off study. Reasons for withdrawal will be documented.
4. Noncompliance with protocol guidelines (participant removed at discretion of Principal Investigator).
5. Disease progression
6. Death

3.8 FOLLOW-UP EVALUATIONS

After subjects have stopped taking the study medication for any of the reasons listed in Section **3.6**, they will be seen at NIH, if logistically feasible, for a safety visit within 4-5 weeks for Lead-in mCRPC cohort and 6-8 weeks for neoadjuvant cohort of drug discontinuation. The safety assessments may be performed by a local physician and laboratory if participants unable to return to the NIH Clinical Center at this time.

The following assessments will be performed at the follow up safety visit:

- History and Physical Examination
- CBC with differential and platelet count, prothrombin time/INR, activated partial thromboplastin time
- Serum chemistries (Na+, K+, Cl-, CO2, BUN, creatinine, glucose, AST/ALT, bilirubin, calcium, phosphorous, albumin, magnesium, alkaline phosphatase, LDH, ionized calcium, amylase, lipase, total protein, uric acid), TSH
- Serum PSA level
- Adverse event reporting

After the safety visit, if there are no unresolved grade 3 or higher AEs, we will offer participants the opportunity to enroll on our long term follow up study. If there are unresolved grade 3 – 4 AEs, participants will be followed either at the NIH Clinical Center or by their local physician. In the latter case, we will obtain the physician's record of AEs.

Any scans performed outside of the NIH will also be obtained when possible.

3.9 POST-STUDY EVALUATION

In 2006, the FDA excluded pox virus based vaccine platforms from required long term follow-up. Following this guidance in 2006 we haven't built in long term follow-up for our pox-viral studies as such vectors have not been shown to have a propensity to integrate or reactivate following latency and, in the absence of evidence to the contrary, present a low risk of gene therapy-related delayed adverse events. Therefore no long term follow up is required with this study, though participants will be offered the opportunity to enroll on our long term follow up study.

4 CONCOMITANT MEDICATIONS/MEASURES

Subjects must inform the investigators of the current or planned use of all other medications during the study (including prescription medications, vitamins, herbal and nutritional supplements, and over-the-counter medications).

Anti-emetics, stool softeners and antidiarrheal agents may be administered as required but are not anticipated to be needed and should not be used prophylactically on the first cycle. The selection of the specific antiemetic regimen is at the discretion of the treating physician. Antiemetic regimens will not include steroids.

Other supportive care with blood components, antibiotics, analgesics, general medical therapy, etc., will be delivered as required. Any participants taking antibiotics for an active infection must complete that course of therapy and be free of evidence of further infection before receiving any immunotherapy treatment. Antibiotics for prophylaxis are allowed while on treatment.

Concurrent systemic corticosteroid use (daily or every other day for continued use > 14 days) should be avoided within 14 days before the first planned dose of PROSTVAC. Use of inhaled steroids, nasal sprays, and topical creams for small body areas is allowed. Limited use of steroids is allowed on study (e.g., for immune related adverse events or for premedication for imaging).

Symptomatic anemia should be treated with appropriate red blood cell or erythropoietin support.

Thrombocytopenia should be treated conservatively. In the absence of bleeding or a planned invasive procedure, platelet transfusions should be given for a platelet count below 10,000/mm³. If invasive procedures are planned or the participant develops bleeding, platelet transfusions should be administered in accordance with the standard of practice, usually maintaining a platelet count of > 50,000/mm³.

Any evidence of disseminated intravascular coagulation (DIC), hemolytic uremic syndrome (HUS), or thrombotic thrombocytopenic purpura (TTP) including thrombocytopenia, hemolytic anemia, renal failure, fever or neurologic changes should be thoroughly evaluated and closely monitored and supported as clinically indicated.

A standard of care radical prostatectomy will be performed between week 5 and week 12 to allow for logistical constraints, but ideally as close to week 9 as possible. This may occur at NIH or at an outside institution. Surgical specimens will be requested for research use (Section 5).

